**Adherence Connection for Counseling, Education, and Support (ACCESS)-II**  
**NYU Principal Investigator (PI) - [name]**  
**Protection of Human Subjects**  
**January 31, 2024**

The primary objective of the proposed clinical trial, **Adherence Connection for Counseling, Education, and Support (ACCESS)-II**, is to test the efficacy of ACCESS-II on antiretroviral treatment (ART) adherence and HIV-viral load in Black and Hispanic HIV-infected (HIV+) adolescents and young adults (AYA), ages 18-29 years (N=120) using a longitudinal (12 and 24 week outcomes), two-group, randomized controlled trial (RCT). Participants in the intervention condition will use videoconferencing to connect synchronously with trained HIV+ peer health coaches who will deliver eight weekly, 60-minute cognitive behavioral/motivational sessions for improved ART adherence. Participants in the control will connect asynchronously to a web-based HIV ART adherence education condition.

**In accordance with policy from the National Institutes of Health (NIH) on the use of single institutional review board (IRBs) for multi-site research, Principal Investigator (PI)/NYU will be utilizing a single IRB for this multi-site research project. NYU will be the IRBs of record for the ACCESS II RCT.**

## **Risks to Human Subjects**

### **Human Subjects Involvement, Characteristics, and Design**

#### ***Overview of aims, research design and number of participants to be enrolled:***

**AIM 1.** Evaluate the effect of ACCESS-II on the primary outcomes of self-reported ART adherence and HIV viral load and secondary outcomes of self-efficacy, HIV knowledge, HIV stigma, psychological distress (depression, anxiety, posttraumatic stress), social support, and substance use.

**Primary hypothesis.** Black and Hispanic HIV+AYA participants in the ACCESS II RCT intervention condition will have greater ART adherence and HIV viral load reduction, when compared to the asynchronous web-based HIV ART adherence education control.

**AIM 2.** Identify which socioecological factors (self-efficacy, HIV knowledge, HIV stigma, psychological distress (depression, anxiety, posttraumatic stress), social support, and substance use) are associated with ART adherence and HIV viral load outcomes.

**The goal** is to characterize adherence phenotypes among Black and Hispanic HIV+AYA participants of ACCESS II.

**Research Design and Intervention – Overview.** To achieve these aims, a longitudinal (12 and 24- week study outcomes), two-group, randomized controlled trial (RCT) is proposed in a sample population of 120 perinatally and behaviorally, HIV+ AYA (ages 18-29 years). Participants in the intervention condition will use videoconferencing to connect synchronously with trained HIV+ peer health coaches who will deliver eight weekly, 60-minute cognitive behavioral motivational sessions for improved ART adherence. Participants in the control will connect asynchronously to a web-based HIV ART adherence education condition.

Study participants will access the intervention and control conditions outside of the clinical setting using study funded smartphones. Self-reported adherence and viral load (extracted from the medical records) of study participants will be measured, and uploaded to REDCap. Knowledge about ART, adherence self-efficacy, HIV stigma, social support, psychological distress (depression, anxiety, posttraumatic stress) and substance use will be measured using survey measures. Statistical analyses will be computed to assess the potential impact of ACCESS on adherence and HIV viral suppression, and will also be computed to assess changes in knowledge about ART, adherence self-efficacy, HIV stigma, social support, psychological distress (depression, anxiety, posttraumatic stress), and substance use among participants in both the intervention and control conditions.

**Characteristics of the Human Subjects.** Characteristics of the target study population include ethnic minority, Black and Hispanic HIV+AYA; both males and females are eligible for participation. The specific criteria for participation in the study are listed below.

#### ***Inclusion criteria for participation in this study are:***

- HIV seropositive status (perinatally and behaviorally infected youth)
- Ages 18-29 years

- English speaking
- Currently being prescribed an oral antiretroviral treatment regimen
- Evidence of difficulty with virologic suppression (*detectable quantitative HIV serum viral load  $\geq 20$  copies/ml*)
- No neuro-cognitive deficits which would impede participation in videoconferencing sessions or completion of study measures

**Expected Number of Human Subjects.** We determined the study sample size (N=120) based on our prior K23 research and the best available peer-reviewed evidence. Pilot findings from our K23 showed that the average change over one year was a  $0.28 \log^{10}$  reduction (47.5%) in viral load; thus, the average change was in the desired direction. The interval estimate was consistent with small increases in VL, no change, and larger reductions (CI=95% -0.12, 0.66), which is why a larger study which includes phenotyping is needed. We compared a  $0.28 \log^{10}$  viral load reduction to other US-based mHealth adherence interventions with HIV+AYA including our published state of the science integrative review on technology-enabled adherence interventions conducted in the US with HIV+AYA. Many studies are small pilots and do not include virologic outcomes or the intervention had no significant effect on viral load. Among included RCTs, findings from one study using text-messaging reminders (N=105) showed no post intervention effect on HIV viral load. Results of a multisite RCT testing a two-session computer-delivered motivation intervention (N=76) showed a small post-intervention decrease in viral load (Cohen's  $d = 0.19$  at 6 months). Another smaller RCT (N=37) testing cell phone support demonstrated a statistically significant reduction in viral load at 24-weeks ( $p=0.002$ ) and 48 weeks ( $p=0.04$ ). A recent RCT study protocol testing an mHealth adherence intervention (texting and videoconferencing) with HIV+ youth was powered at 85% to detect a 25% difference in virologic suppression at 12 weeks.

Therefore, our projected sample size ( $n = 120$ , 60 per treatment condition) will achieve 80% power to detect medium to large effects ( $d = .44$  to  $.57$ ) for  $\log^{10}$  viral load reduction associated with treatment (assuming within-individual correlations  $\rho = .3$  to  $.6$ ). We will have 80% power to detect differences of 23% to 25% in viral load suppression between treatment groups (assuming viral load suppression in the control group of 20% to 50%) and small correlations between primary outcomes and individual and interpersonal influences on ART adherence (Pearson's  $r = .25$ , Spearman's  $\rho = .27$ ). Based on pilot findings showing a 32.1% increase in adherence (large effect  $d = 1.12$ ), the current study would have more than 90% power to detect a comparable effect (assuming within subject correlations of  $\rho = .3$  to  $.6$ ).

**Rationale for Involvement of a Vulnerable Population.** The ACCESS adherence intervention was designed to address the serious and lifelong challenge of antiretroviral adherence in HIV+ AYA. **The target population of ACCESS II RCT is ethnic minority AYA ages 18 to 29 years**, as the incidence of HIV-infection in this cohort is alarming. Among the 100,000 HIV+ AYA, 70% are represented by Blacks and Hispanics. Nearly 23,000 new cases of HIV were reported among Black and Hispanic AYA in 2017, despite availability of effective antiretroviral therapy (ART) for decades. Treatment recommendations for infected individuals include lifelong treatment with antiretroviral medications. Suboptimal ART adherence (<90%) is described among 39% of this cohort, and only half are virologically suppressed (viral load  $<200$  copies/ml), leading to high risk for sexual transmission. Innovative and robust ART adherence strategies are critical to reducing these ethnic/racial minority health disparities. To date, adherence interventions among HIV+AYA have been of limited in number and efficacy.

**Assignment to a Study Group.** The proposed ACCESS II RCT uses a two group, parallel, longitudinal study design. Participants will be randomized to the ACCESS synchronous peer

intervention or the asynchronous web-based HIV ART adherence education control. Block randomization will be used; the randomization scheme will be developed by the biostatistician and implemented in Research Electronic Data Capture (REDCap) to ensure that assignment to treatment condition is evenly distributed within each site. Study details will be reported using guidelines defined by the Consolidated Standards for Reporting Trials (CONSORT). This will include items defined in the checklist for parallel randomized trials and a flow chart detailing enrollment, allocation, follow-up, and analyses.

**Collaborating Sites.** After approval from designated institutional review boards, HIV+ ethnic minority AYA will be recruited from the adult and pediatric HIV centers within Jacobi Medical Center, (North Central Bronx Network), and BronxCare Health System. BronxCare is only engaging in recruitment and not directly engaging in the consenting process. [name] will be designated site investigator at Jacobi Medical Center and North Central Bronx Network and [name] will be the designated site collaborator for recruitment at BronxCare Health System.

Jacobi Medical Center is part of the North Central Bronx Network, which includes a local affiliate, the HIV outpatient center of North Central Bronx (please see facilities and resources). The North Central Bronx HIV outpatient center treats 600 HIV+ adults and adolescents, offering an addition recruitment resource through their collaboration with Jacobi Medical Center.

BronxCare Health System is the largest voluntary, not-for-profit health and teaching hospital system serving the South and Central Bronx (please see facilities and resources).

IRB approved recruitment materials (i.e. pamphlets and fliers) will be posted in select Community-Based Organizations (CBOs) and Community Events serving HIV+ AYA throughout the City of New York. With assurances from the CBOs, these IRB approved recruitment materials may be posted in their physical space and posted electronically (social media pages, newsletters, website, etc.).

**Compensation.** Care was taken in the construction of the incentive schedule to prevent any coercion bias, yet participants will be compensated for their time. We will compensate participants with the support of ClinCard (<https://www.clincard.com/>). The schedule for compensation of completed study activities is as follows: \$25 cash for completion of the consent process and basic demographics; \$100 cash for the completion of baseline, 12 and 24-week data collection/testing; \$25 cash for return of the study phone upon completion (\$350 total possible compensation).

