The ACCESS II RCT will use EPIC to identify potential participants. A DataCore request will be placed by an ACCESS II RCT study team member (i.e. Principal Investigator, Project Manager) to identify potential participants based on study inclusion/exclusion criteria. The following data will be requested: Patient Name (first and last), Patient Date of Birth, Patient Contact Information, Language Spoken, Date of Last Clinic Visit, Medical Provider Contact Information, and HIV Viral Load (we will be requesting data for patients with a viral load greater than or equal to 20 copies/ml). Only IRB Approved Key Personnel from the ACCESS II RCT will have access to the DataCore/EPIC data. Any recruitment information sent by NYU Langone Email will utilize Send Safe email ("[SENDSAFE]").

Once potential participants have been identified, the ACCESS II RCT study team (i.e. Principal Investigator, Project Manager) will notify them as follows:

- Provide their treating physician (TP), Nurse Practitioner (NP), or their support staff (i.e. social workers, case coordinators a list of potential participants, recruitment fliers and pamphlets, and written and oral script to use when informing potential participants of the ACCESS II RCT.

OR

- Notify the TP, NP and/or their support staff that the ACCESS II RCT study team will directly contact potential participants, after their visit with the TP, NP and/or their support staff in the clinic/telemedicine setting. Participants will be contacted either in person at NYU provider visits, by phone and/or text, or SendSafe email. Potential participants will be notified by the TP, NP and/or their support staff that the ACCESS II RCT study team member will be contacting them.

OR

- Directly contacting the potential participant (via phone call, text, email) using the contact information provided by the DataCore list generated, to inform them of the ACCESS II RCT and gauge their interest. An oral or written script will be used by the ACCESS II RCT Research Team Member when contacting the potential participant.

Once contact is made with a potential participant, IRB approved recruitment language will be used to communicate the reason why they are being contacted.

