**Importance of the Knowledge to be Gained.** One million US individuals are HIV+ including 100,000 AYA, ages 15-29 years. Black and Hispanic AYA are disproportionately represented in the US HIV health crisis. Antiretroviral therapy (ART) effectively treats HIV infection and prevents HIV-related morbidity, mortality and sexual transmission, but improved health outcomes are related to behavior: benefits of ART are directly proportional to levels of adherence. Optimal adherence is defined as 80 to 90% for protease-inhibitor-boosted regimens and greater than 90% for un-boosted regimens. Black and Hispanic HIV+AYA have the lowest rates of ART adherence; nearly 40% reported suboptimal adherence (<90%) during the past week. Virologic estimates show that only half of US AYA (ages 13-24 years) achieved suppression (HIV RNA level of <200 copies/ml). Black and Hispanic HIV+ AYA are at high risk for virologic failure during their entire HIV treatment course, even after a period of virologic suppression. Persistent HIV viremia due to suboptimal ART adherence is a primary contributor to the increasing number of HIV infections. A shift in the current approach to ART adherence support is desperately needed.

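### The entry criteria do not separate adherence-related viraemia from a recent ART start, restart or switch, and time on ART is not among the data to be collected

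*Combined protocol and SAP*

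**What the plan says.** The inclusion criteria ask for "Currently being prescribed an oral antiretroviral treatment regimen" and for "Evidence of difficulty with virologic suppression", the second defined only as a detectable viral load of at least 20 copies/ml. The remaining criteria cover HIV status, age, language and cognition. There is no minimum time on ART, stable-regimen condition, repeat value or look-back period.

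The record search under Recruitment and Informed Consent uses the same threshold: "we will be requesting data for patients with a viral load greater than or equal to 20 copies/ml". Its list of requested items includes no ART start or regimen date. Exclusion criteria are mentioned there, but none are listed.

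Assignment to a Study Group describes blocks intended "to ensure that assignment to treatment condition is evenly distributed within each site" and names no other balancing factor. Sources of Materials does not list time on ART among the measures. The overview of the analyses names no model or covariate.

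The intended target appears under Importance of the Knowledge to be Gained: "Persistent HIV viremia due to suboptimal ART adherence is a primary contributor to the increasing number of HIV infections". The primary hypothesis is a randomised contrast, that the intervention group "will have greater ART adherence and HIV viral load reduction, when compared to the asynchronous web-based HIV ART adherence education control".

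**The concern.** In a person established on ART, a detectable viral load may reflect difficulty with adherence. In a person who began or changed treatment a few weeks ago it may show only that the drugs have not yet had time to work. The rule admits both, so it does not measure what its label says.

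Recent starters would tend to show a large viral load fall by weeks 12 and 24 in either arm. In Aim 1 that leaves less room for the intervention to show a difference and widens the spread of change. In Aim 2, which relates self-efficacy, stigma, distress and other factors to viral load and seeks adherence phenotypes, a treatment-start fall can be read as an adherence response. If the dates are never collected, neither effect can be measured or corrected afterwards.

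**Working it through.** **Inputs from the documents.** N = 120, "60 per treatment condition"; 80% power claimed for a difference of 23 to 25 percentage points in suppression, with control rates of 20% to 50% (Expected Number of Human Subjects).

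**Assumptions, none of them in the documents.** Two-sided alpha 0.05; share of recent starters or switchers f = 5%, 10% or 20%; 90% of them suppress in either arm; their arm-independent fall D is 1.5 to 2.5 log10; SD of log10 change is 1.0 in everyone else.

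**Step 1: reproduce the plan's figure.** With n = 60 per arm and p̄ the mean of p1 and p2,

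power = Φ{ [ |p1 − p2| − 1.96 √(2p̄(1 − p̄)/n) ] / √( p1(1 − p1)/n + p2(1 − p2)/n ) }.

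- 20% v 43%: (0.23 − 0.1662)/0.0822 = 0.776, power 78.1%.
- 30% v 55%: 79.9%. 40% v 65%: 79.0%. 50% v 75%: 81.6%.

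The stated 80% reproduces to within 2 points, with no visible margin.

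**Step 2: suppression with recent starters included.** Each arm's rate becomes (1 − f)p + 0.9f, so the difference shrinks by the factor (1 − f).

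| f | 20% v 43% becomes | Power | 50% v 75% becomes | Power |
|---|---|---|---|---|
| 0 | 20.0% v 43.0% | 78% | 50.0% v 75.0% | 82% |
| 5% | 23.5% v 45.4% | 72% | 52.0% v 75.8% | 78% |
| 10% | 27.0% v 47.7% | 65% | 54.0% v 76.5% | 74% |
| 20% | 34.0% v 52.4% | 53% | 58.0% v 78.0% | 65% |

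**Step 3: spread of log10 change.** SD = √(1 + f(1 − f)D²).

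| f | D = 1.5 | D = 2.5 |
|---|---|---|
| 5% | 1.05 | 1.14 |
| 10% | 1.10 | 1.25 |
| 20% | 1.17 | 1.41 |

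The SD therefore rises by about 5% to 41%.

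**Step 4: dilution and spread together on the log10 scale (illustration).** Take an effect of 0.57 in everyone else, none in recent starters, and D = 2. Power is 88% at f = 0. At f = 10% the effect is 0.57 × 0.9 = 0.513 and the SD is √(1 + 0.09 × 4) = 1.166, giving 67%. At f = 20% they are 0.456 and 1.281, giving 50%. The 88% is not the plan's own figure: its range d = .44 to .57 depends on a model, alpha and attrition that are not stated and could not be matched exactly. Nothing here depends on that range.

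**Step 5: is the primary comparison biased?** In 20,000 simulated trials with no treatment effect, f = 20% and D = 2, the mean arm difference was 0.00 log10 and the type I error 5.2%. Each arm nevertheless fell by 0.20 × 2 = 0.40 log10 on average. The contrast between arms is protected; change within an arm is not.

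**The case against.** A reader might infer that the treatment-start fall is mixed into the estimated intervention effect. The documents do not support that. The hypothesis is a concurrent randomised comparison, the fall is expected in both arms, and Step 5 shows no bias and a nominal type I error.

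A reader might also fear that an uneven split imitates an effect. With 12 recent starters among 120, a split of 8:4 or worse has probability 0.36, and at D = 2.5 an 8:4 split shifts the difference by 4 × 2.5/60 = 0.17 log10. That is ordinary sampling error, already carried by the standard error, and counting it beside the larger SD counts one source twice. Nor is the pilot's 0.28 log10 the right yardstick, because it is an average change over one year and not a between-arm difference.

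Other points carry weight. The share of recent starters is unknown and may be small. A fall after starting ART still depends on taking it, so assuming no intervention effect in these people is pessimistic. People restarting after a lapse may well belong to the target population, and broad entry is a defensible choice. Under Consenting Procedures the medical team pre-identifies eligible patients and could pass over a very recent starter, although no written rule asks for this. The assumed rise in control suppression, for example from 20% to 27% at f = 10%, stays inside the plan's 20% to 50% range.

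These arguments tell against narrowing entry. They do not tell against recording the dates: dilution remains whatever the control rate, and Aim 2 gains nothing from randomisation.

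**Conclusion.** The point holds as a gap in data collection and analysis, not as a bias in the primary comparison. The criteria cannot tell viraemia from difficulty with adherence apart from viraemia after a recent start, restart or switch, and no section plans to record the information that would separate them.

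The losses in Aim 1 are those of Steps 2 and 3. At an assumed 10% share, suppression power falls to 65% or 74%, and the SD of log10 change rises by 10% to 25%. These sizes rest on the assumed share, 90% suppression, fall and base SD; with few recent starters the loss is small. For Aim 2, the phenotypes and within-arm change, the direction of any distortion cannot be known without the dates.

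A reader might infer that the trial must impose a minimum time on ART. The documents do not settle that. It would narrow recruitment and set a clinical threshold, and the decision belongs to the sponsor.

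**What to change.** 1. Add two items, ART start date and current-regimen start date, to the chart extraction described for viral load in Sources of Materials and to the eligibility source documents that Consenting Procedures already sends to REDCap.
2. Define recent start or switch as a yes/no variable, treating a restart as a start, with a cut-off fixed by the study team before outcome data are examined.
3. Prespecify adjustment for it in the viral load comparison and in the Aim 2 models.
4. Report a sensitivity analysis excluding these participants. Because the variable is fixed before randomisation, the exclusion leaves a randomised comparison, on a smaller sample.

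Adjustment can recover much of the precision lost through the larger SD. It does not undo the dilution, which is why the sensitivity analysis is also needed.

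The cost is two more chart dates per participant and one more covariate. Recruitment and eligibility are untouched, and for participants already enrolled the dates can be sought retrospectively from the chart.

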**Social support** and isolation will be measured with the Adolescent Trials Network (ATN) iTech short measure of the Patient-Reported Outcomes Measure Information System (PROMIS) Social Relationship scales.

**Psychological distress** is operationalized as depression, anxiety and posttraumatic stress. Measurement of these variables is described below.

**Depression** will be measured with the Patient Health Questionnaire (PHQ-9). The PHQ-9 includes 9 items from the DSM-IV criteria for depression with scores on a 4-point Likert scale (0=not at all, 3=nearly every day). Depression is scored as mild, moderate, moderately severe, and severe using composite scores of 5, 10, 15, and 20, respectively. Higher scores are associated with decreased functional status as measured by the SF-20 and scores  $\geq 10$  have a sensitivity and specificity of 88% for major depression. The measure has been used among HIV+ AYA in the United States with a Cronbach's  $\alpha$  of 0.89.

**Question 9 on the PHQ-9 reads:** “Over the past 2 weeks, how often have you been bothered by any of the following problems?..Thoughts that you would be better off dead or of hurting yourself.” If a participant responds “several days”, “more than half the days” or “nearly every day” to this PHQ-9 question at any of the scheduled visits (baseline, 12 or 24-weeks), the project manager will contact the lead PI ([name]) and contact PI at NYU([name]) for guidance.

More specifically, if the participant is at imminent risk for suicide, law enforcement will be notified by Drs. [name] or [name], who will call 911. [name] ( contact PI and licensed clinical psychologist) and [name] (board certified/licensed pediatric nurse practitioner) will also Zoom into the videoconferencing session for crisis management. Full details of managing adverse events are described on pages 15-20 in the Data and Safety Monitoring Plan.

**Generalized anxiety disorder (GAD)** will be measured with the Generalized Anxiety Disorder - 7 (GAD-7). The measure has demonstrated validity and includes 7 items about symptoms in the past two weeks. Scores  $\geq 10$  indicate a probable case of GAD, with scores  $\geq 15$  considered to be severe. Higher scores on the GAD-7 are associated with decreased functional status as

measured by the SF-20. The GAD-7 has demonstrated validity and has been used among HIV+ AYA in the United States with a Cronbach's  $\alpha$  of 0.86 to 0.87.

**Posttraumatic stress disorder (PTSD)** will be measured with the Primary Care-PTSD Screen-5 (PC-PTSD). The PC-PTSD is a brief measure using four-items to screen for symptoms of PTSD (re-experiencing, numbness, hyperarousal and avoidance behaviors) in primary care or ambulatory settings. Total scores range from 0 to 4 with a score of 3 or greater indicating probable or positive screen for PTSD. The tool has been used among HIV+ AYA in the United States.

**Substance use** will be assessed with a modified ATN designed for use in clinical settings. The measure will assess use of tobacco, alcohol, marijuana and other drugs (i.e., cocaine or crack, amphetamine type stimulants, inhalants, sedatives, hallucinogens and opioids). The modified measure will assess substance use frequency, substance use related problems (i.e., health, social, financial), interference with functional status, concern from others regarding substance use, and failure to cut down on substance use.

**Client Satisfaction and Ease of Use** of the web-based platform (Rise) will be assessed by the participants enrolled into the control condition of the study during their eighth (last) session, using a modified Client Satisfaction Questionnaire and Perceived Ease of Use Scale. The measure will be used to assess the participant's satisfaction with the support and education received from the eight sessions in the web-based platform, along with the overall ease of use in operating and functioning the web-based platform over the eight sessions.

**Study funded Smartphone** questionnaire will assess smartphone ownership of participants and the feasibility of attending and completing the ACCESS II RCT study activities with the study funded smartphone. This 13-item questionnaire will assess how easy or difficult the study funded smartphone made it to communicate with the research team, to complete study activities and overall ease of participation in ACCESS II. This questionnaire will be used to determine participant's need for study funded smartphones.

Both viral load and self-reported adherence assessments of medication are assessed as a routine part of medical treatment, and therefore should pose no additional risk. Adherence self-efficacy is not routinely collected and may pose risk of embarrassment due to real or perceived low adherence self-efficacy. HIV Stigma will be measured with the HIV Stigma Scale and is also not routinely measured in clinical care and may also cause risk of discomfort. Mental health measures such as the PHQ-9 (depression), GAD-7 (anxiety), and PC-PTSD (trauma) are also not a routine component of clinical care. As such, there may be risk of discomfort and/or embarrassment. The project manager(s) will be made aware of this potential during training. We have delineated study procedures to manage any emotional discomfort in this protocol on pages 17-19. Social support and substance use are routinely assessed in clinical practice and therefore should not pose any risk of discomfort or embarrassment. However, we will implement training procedures for data collection to minimize all potential risk of discomfort. We have also selected study measures that are psychometrically valid, reliable and tested in HIV+ populations. Only ACCESS II RCT team members will have access to data collected and stored data will be protected as described in the confidentiality section.

